5.3 LIFESTYLE CONSIDERATIONS

N/A

5.4 SCREEN FAILURES

There are no screening requirements or restriction from participation.

5.5 STRATEGIES FOR RECRUITMENT AND RETENTION

Recruitment of health funds will be communicated through intermediaries from union leadership and union organizations within the construction trades. Prior to the start of the study, three union health funds had provided verbal consent to participate. Each enrolled health funds must be willing to participate in all facets of the project, including data collection, and trial of the intervention.

The research team will work with each health fund to identify potential means to invite members to complete the worker survey. Possible methods for survey recruitment include distributing an online survey link via email or text message, posting a survey link in union newsletters, or collecting paper surveys at union meetings or training schools. Access to the survey will be provided through a QR code or electronic link to a Redcap survey which is a secure, web-based data collection tool. Worker survey data collection will be cross-sectional in nature and therefore we do not plan to follow individual workers overtime. Participants will be given the option to refuse participation without any repercussions to their employment, health benefits, or standing in the union.

The survey will take approximately 10 minutes to complete. There will be no incentives offered to participate.

Each health fund will seek completion of 300 surveys at two time points, baseline and 6-months for a total of 900 surveys from three health funds. The expected enrollment will reflect the demographics of the population, with approximately 8% females, and 10% non-Caucasian. The age range will be from 18 years with no upper age limit, although the majority of the sample will range from 18-65 years. The data from this trial will be used to compute statistical power for a future study, should the feasibility trial be successful.

6 STUDY INTERVENTION(S) OR EXPERIMENTAL MANIPULATION(S)

6.1 STUDY INTERVENTION(S) OR EXPERIMENTAL MANIPULATION(S) ADMINISTRATION

6.1.1 STUDY INTERVENTION OR EXPERIMENTAL MANIPULATION DESCRIPTION

The intervention is a set of evidence-based guidelines developed by the research team, with formative work and review by subject matter experts, and stakeholders from the construction industry, many of whom have implemented the policies, programs and benefits suggested in the guidelines. The intervention will provide recommendations across the continuum of disease from prevention (no opioid use), through treatment and recovery. It will also cover the topics for different roles including human resources, upper management, front-line supervisors and healthcare providers involved with the monitoring and treating drug-related issues.

The intervention is intended to be used by the organization, union health fund that provides the health benefits and programs for the union members. The health fund has the fiduciary responsibility to provide health policies, programs, and benefits to maximize the health of the members. The health fund must receive approval for health initiatives from the Labor-Management board of trustees. The target of the intervention is the union members, who are the subjects of the health fund policies, programs, and benefits. The outcomes of the study will be measured by the clinical health claims, and self-reported behaviors of the union members.

6.1.2 ADMINISTRATION AND/OR DOSING

The health fund administrator will meet with the Principal Investigator from the research team to participate in a baseline interview to explore the current policies, programs and benefits offered by the health fund to protect the members from opioid misuse and opioid use disorder. The baseline health fund interview will cover the company background, attitudes and beliefs toward opioids, health fund policies and programs, (written policies, drug testing, medical health benefits, behavioral health benefits, pharmacy benefits, member assistance program, legal considerations, employee education on opioid risks, supervisor training related to opioid use, culture of care of the union, collective bargaining agreement related to substance and opioid use disorder, and plans to change policies and programs related to opioids and substance use). **The baseline interview guide can be found in the Additional Information section: R34 Aim 3 Health Fund Baseline Interview Guide_051222.**

After all baseline data collection is completed, the intervention will be initiated. The intervention will include one-hour monthly meetings by Zoom scheduled at a convenient time for the health fund

administrator and the Principal Investigator. At the initial meeting, the health administrator will be introduced to the guidelines and asked about what plans they currently have to change. A copy of the guidelines used in the trial can be found in the Additional Information section: v3.0_WashU_Opioid Prevention Program in Construction_07062022.

At each follow-up monthly meeting, the researcher will ask information from the Monthly Health Fund meeting script_follow up found in the Additional Information section. The intervention meetings will be held over a 6-month period.

The meetings will provide an opportunity to discuss barriers to implementation and share new ideas and strategies. The health fund administrator will be encouraged to build a team to support the development and implementation of the plan ideas (as discussed in the guidelines). The meetings will also provide an opportunity to discuss the analysis of the administrative claims, and results of the worker surveys.

6.2 FIDELITY

6.2.1 INTERVENTIONIST TRAINING AND TRACKING

The intervention will be delivered by the Principal Investigator. Each meeting will cover the progress the health administrator has made toward implementing their plan, and whether the health administrator found new ideas or resources for their plan from the guidelines. The follow-up monthly meeting will be scheduled at the end of the prior meeting with reminders sent out to the health administrator 2 days in advance of the meeting. Interim communications will be made by email as needed.

6.3 MEASURES TO MINIMIZE BIAS: RANDOMIZATION AND BLINDING

This study does not involve randomization nor blinding.

6.4 STUDY INTERVENTION/EXPERIMENTAL MANIPULATION ADHERENCE

Monthly meeting attendance will be logged in OneNote (a project management log) with cancellations and reasons for cancellations as this will be important information to consider for the feasibility of a future trial.

6.5 CONCOMITANT THERAPY

N/A

6.5.1 RESCUE THERAPY

N/A

7 STUDY INTERVENTION/EXPERIMENTAL MANIPULATION DISCONTINUATION AND PARTICIPANT DISCONTINUATION/WITHDRAWAL

7.1 DISCONTINUATION OF STUDY INTERVENTION/EXPERIMENTAL MANIPULATION

This feasibility trial is designed to learn what barriers exist for participation in the trial, across all study activities throughout the study process:

- the initial recruitment of health funds,
- enrollment of health funds that complete the study eligibility (data transfer and use agreement)
- collection of baseline data including administrative claims and worker surveys,
- completion of the baseline interview with the health administrator (about existing policies, programs, and benefits related to substances and opioids),
- attendance to monthly intervention meetings for 6 months,
- follow-up data collection on worker surveys at 6-months,
- final data collection at 12-months (time permitting).

The feasibility trial will be discontinued at the end of the 6-month intervention, or if all enrolled health funds drop out of the study, or if no health funds are enrolled with adequate time in the study period remains to complete the intervention (of at least 6-months).

7.2 PARTICIPANT DISCONTINUATION/WITHDRAWAL FROM THE STUDY

A health fund may be withdrawn from the study if they stop participating or request to drop out.

No participant will be withdrawn from the study. Participants may choose to not complete the worker survey. The researchers may drop a participant's survey from analysis if more than half of the items are not completed.

7.3 LOST TO FOLLOW-UP

The health fund may be lost to follow up if they stop attending meetings.

The participant data is collected as cross-sectional data so no participants will be lost to follow-up.

8 STUDY ASSESSMENTS AND PROCEDURES

8.1 ENDPOINT AND OTHER NON-SAFETY ASSESSMENTS

At baseline, recruited union health funds will be asked to agree to several activities before they are enrolled in the study. These include 1) sign a data transfer and use agreement (DUA) with the Washington University research team, 2) willingness to review the Workplace Guidelines to Prevent Opioid Abuse in the Construction Trades" and implement changes to their organizational policies, programs, and benefits to reduce opioid misuse and opioid use disorder among their members, 3) participate in a series of study-related meetings to discuss their current program and plan for changes, 4) provide administrative claims as outlined in the DUA, and 5) communicate invitation to all members to complete a worker survey for the study. The partners were asked to enroll for a minimum of 6-months but preferable 12-months of activities.

Once the DUA was signed and the union health fund was enrolled, and the administrator or their representative was asked to participate in an interview to discuss their knowledge and attitudes toward OUD, describe their existing workplace opioid policies and programs and the date of adoption or implementation, and any changes to their policies or programs underway or plans for future changes. The interview also asked questions about participation rates in programs for workers, adherence to and enforcement of policies, and the methods for disseminating programs. See "R34 Aim 3 Health Fund Baseline Interview" in the Additional Information Section.

The other baseline data collection included the administrative claims data and member "worker surveys".

The union health fund administrator was asked to share a pre-specified set of variables from their medical and pharmacy claims and covering the period from May 2019-May 2022. See the list of requested variables from the administrative datasets in the Additional Information Section in the file called "Data Variables List for opioids project_052322". The study team had the administrator to share a sample of their variables for review by study team. Once the variables were agreed upon, the administrator was asked to share the de-identified datasets with a linking variable so the data could be linked without using an employee id or social security number. The data would be shared under a waiver of consent. All data was stored on a secure network. Only members of the research team had access to the data. The statistician and PI worked with the health fund staff to insure they had a good understanding of each variable (and units of each) and were able to create a database that aligned with the variables needed for analysis. See the data management section and analysis plans below.

The participating union health funds were asked to distribute a link for a Redcap survey to a representative sample of their members to collect 300 completed surveys. All members of the union were eligible but member participation was voluntary. The health fund recruited the member using methods determined by them to be most successful to reach the members and encourage participation. These methods included email, newsletter, and verbal invitations. Members were invited to participate but they were allowed to take as much time as they want to consider participation in the study. The health fund did not know which members participated in the survey. The surveys were accessed through a QR code or survey link shared through health fund communications. The Redcap QR code or survey link could be accessed through a computer or on an apple or android device. The first page of the survey showed the consent information (see Consent Document). The member had the option to consent by advancing to the survey or to decline by exiting the survey. There was no written consent and participants were not paid to participate. The brief survey asked about the members' knowledge of their health fund's benefits and policies, attitudes toward use of opioids by self and others, employment status, participation in union programs including Employee Assistance Program (EAP), and health-related productivity using widely used survey instruments. We did not collect names or any other identifying information and the survey took about 5-10 minutes to complete. A copy of the members "R34 AIM 3 Worker Survey" may be found in the Additional Information Section.

The data was collected in the Redcap software program at Washington University. The electronic information was stored on a password protected, secured server at Washington University. Only member of the research team had access to the data. Only summarized information from the worker surveys was shared with the health fund. During the period of data collection, the research team reviewed the demographics and counts of the survey, to encourage continued data collection if the desired number of surveys was not collected or the data did not represent the characteristics of the workforce.

After completion of the baseline data collection, the research team met with the union health fund administrator to introduce the intervention. The guidelines are shown in the Additional information section (v3.0_WashU_Opioid Prevention Program in Construction_07062022). The team and health fund met on a recurring monthly basis for 6 months. The goal of the meetings was to discuss the health fund's plan for changes to their opioid prevention program. A series of questions were discussed to review the progress on the plan, and to discuss how the guidelines were used to support the planned changes. Following the items in the REAIM framework, the discussion included "what" was changed or planned to be changed, the implementation strategies for adoption of the changes, and barriers and success for implementing the change. All meetings were virtual (primarily over Zoom) and scheduled a month in advance, with a reminder sent out 2 days before the meeting.

Data Management: The following are the list of steps taken to manage the administrative health claims and worker surveys. The final databases were used to compute the results for outcomes.

See the “Data management of Administrative Health Claims and Worker Surveys” in the Additional Information section.

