The objective of this trial is to evaluate the feasibility of implementing the workplace opioid guidelines in union health funds of the construction trades by measuring the implementation and effectiveness of health,	The primary endpoint(s) include a change in a) Proportion of workers with opioid misuse, opioid use disorder and opioid overdose from administrative data and b) Proportion of workers with opioid misuse from worker surveys	Administrative claims data covers all the majority of the union members as most members are eligible for these benefits. Therefore, the data more accurately reflects the proportion of the workforce who have misused opioids or received a diagnosis for opioid use

OBJECTIVES	ENDPOINTS	JUSTIFICATION FOR ENDPOINTS
behaviors, and attitudes toward opioids.		disorder. These metrics are useful outcomes to show the longer term impact of policies and benefits provided through the union health fund.
Secondary The secondary objective(s) are goals that will provide further information on the use of the intervention.	Secondary endpoints include a change in behaviors and attitudes in response to the intervention and will include a) Proportion of workers with lost time from worker surveys and b) the proportion of workers who are willing to seek help from opioid misuse from worker surveys.	The worker survey data shows the perceived behaviors reported by the respondents. These respondents will be compared to the demographics of the population to explore potential bias by workforce characteristics. These outcomes show the intermediate impact of policies and programs provided through the union health fund.

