9.2 SAMPLE SIZE DETERMINATION

There were no power sample calculations for this study as it is a feasibility pilot study. The data generated from this study will inform the power calculations for a future R01, if the pilot study is successful.

We estimated the number of participants needed for surveys from the sample sizes needed to document change over time for similar behavior outcomes from past studies. The data will be collected at two points in time (baseline and 6-months after start of the intervention). We will collect cross-sectional data, and calculate the group-level change pre-post intervention. We will collect 300 surveys for each participating health fund at baseline and at 6-months post-intervention, and at 12-months time permitting. This will be a minimum of 1800 surveys, or 2700 surveys time permitting.

We estimated the number of participants for the administrative data from the membership sizes of union health funds from past studies. In past studies, union health fund members have covered 10,200 members. We estimate we will collect administrative data for 10,200 members for each of three health funds (total of 30,600) members.

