9.3 POPULATIONS FOR ANALYSES

We will calculate descriptive statistics for the full population of the administrative data. The data will include active and retired members from the benefits-eligible group of the period May 2019-May 2022. We will include any member who was continuously benefits-eligible but censor them after they drop eligibility or don't self-pay to continue coverage. All retired members who self-pay will also be included in the analyses.

We will calculate descriptive statistics for those members who complete the worker survey. We will compare the demographics (age, gender, race) of those who completed the survey to the union

membership to see if the two groups (surveyed versus union members) have similar characteristics. This will help assess the feasibility of the survey recruitment methods to obtain a representative sample.

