3. Chronic MSD or recurring acute injuries
4. Other diagnoses

- v. Opioid utilization. Number of workers with:
 1. At least one opioid fill
 2. Ever days supply > 7
 3. Ever MME/day > 50
 4. Ever MME/day > 90
 5. Overlapping Rx
 6. Chronic use (>60 day supply in 90-day period)
 7. Multiple Rx on the same day, same provider
 8. Multiple Rx on the same day, different providers
 9. Misuse
- vi. OUD
 1. N by source (diagnosis, MAT fill, both)

- h. Medical claim/opioid linked data
 - i. Distribution of opioid fills by diagnosis, as captured on linked claim

- b) Worker Surveys
 - a. Worker surveys will be distributed to all members of each health fund at start of project, to collect a sample of 300 surveys. We will collect another sample of 300 surveys after 6 months.
 - b. We will examine the serial cross sectional data (baseline & 6mos) by comparing sample characteristics.
 - Age, x
 - gender, x
 - race, x
 - hisp, x
 - unionbenefits, x
 - employstatus, x
 - time_construction, x
 - months_construction, x
 - constype;x
 - c. We will examine the items related to each of the three outcomes of interest
 - i. Opioid misuse- A “yes” response to either of the following two items:
 1. Did you use the pain medication more than prescribed, or for a longer period than prescribed? [pnmed_longer]x
 2. Have you used prescription pain medications that were prescribed to someone else? [pnmed_othersrx]x
 - ii. Proportion of workers with lost time- A “yes” response to either of the following two items:

1. Please refer to the last 12 months for the following questions: Did you miss any days of work because of your pain or discomfort? [missday_pn]x
2. In the past 12 months, have you gone to work intoxicated, high, or recovering from the night before? [missday_intox] [*possible reduced productivity]x
- iii. Proportion of workers who are willing to seek help
 - 1) their workplace
 1. If I was struggling with a substance use problem... I would be willing to seek help from my supervisor or someone in human resources [help_sup_hr]x
 2. If I was struggling with a substance use problem... I would be willing to seek help from a professional (MAP or behavioral health) [help_prof]x
 3. If I was struggling with a substance use problem... I would be willing to ask a trusted coworker for help [help_coworker]x
 4. Have you attended Alcoholics or narcotics anonymous (AA/NA) group [aa_na_use]x
 5. Have you met with the specialist? [peer_supp_use]x

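### Demographic mismatch can trigger further survey collection, and the demographic match is then used to judge the recruitment methods, with no pre-extension comparison and no report of the extensions

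*Combined protocol and SAP*

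**What the plan says.** Section 8.1 describes in-process monitoring of the worker survey. The team looks at how many surveys have arrived and who has answered, "to encourage continued data collection if the desired number of surveys was not collected or the data did not represent the characteristics of the workforce". Each fund chooses its own way of reaching members.

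Section 9.3 sets out the later comparison: "We will compare the demographics (age, gender, race) of those who completed the survey to the union" membership. Its purpose follows: "This will help assess the feasibility of the survey recruitment methods to obtain a representative sample". Section 3 gives the comparison a second use: "These respondents will be compared to the demographics of the population to explore potential bias by workforce characteristics".

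The target is in Section 9.2: "We will collect 300 surveys for each participating health fund at baseline and at 6-months post-intervention". Section 5.5 expects about 8% women and 10% non-Caucasian respondents.

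The invited group is described in two ways. One sentence of Section 8.1 has the funds "distribute a link for a Redcap survey to a representative sample of their members to collect 300 completed surveys". The list of fund commitments in the same section has them "communicate invitation to all members to complete a worker survey for the study". Section 9.4.1 also invites everyone, and the appended data management document says "Worker surveys will be distributed to all members of each health fund at start of project".

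No section plans a response rate. The schedule in Section 1.2 gives the follow-up survey a window of Day 180±30 and the baseline survey none.

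**The concern.** The characteristics that steer collection are later read as evidence about the methods. If early respondents do not resemble the workforce, the plan allows a push for more. Section 9.3 is then applied to whatever sample results. A good final match could mean that the funds' ordinary channels reach the workforce, or that they did not and extra effort made up the difference. The planned output cannot tell these apart.

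This bears on the trial's own question. Section 4.4 says it is not known whether the survey data can feasibly be collected. Section 7.1 lists survey collection among the activities whose barriers are to be learned. Section 3 says the benefit is to test procedures for a future randomised trial. A planner of that trial needs to know what the first invitation achieved, how many extra rounds followed, and roughly how many members were invited for each completed survey.

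**Working it through.** **The plan's own figure.** 300 surveys × 3 funds × 2 waves = 1,800, and × 3 waves = 2,700, as Section 9.2 states. The 900 in Section 5.5 is 300 × 3 × 1, one wave only; that is a separate item to reconcile.

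**Does the text separate early from final surveys?** Sections 8.1, 9.3 and 9.4.1 and the appended data management document were read together. None restricts the comparison to surveys received before an extension, and none asks for extensions to be recorded or reported.

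**One worked case.** Benchmark 8% women (Section 5.5); exact two-sided binomial test against 0.08. The starting count is an assumption.

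- 12 women in 300 = 4.0%, p = 0.008.
- Add 3 surveys, all from women: 15/303 = 5.0%, p = 0.056.
- Add 13, all from women: 25/313 = 8.0%, p = 1.0.

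A few well-aimed responses therefore remove the signal. An unaimed extension rarely does. From 12/300:

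- Three consecutive women at a 4% response share has probability 0.04³ = 0.00006.
- With 100 more surveys at 4%, p exceeds 0.05 with probability 0.7%.
- With 100 more at the true 8%, it exceeds 0.05 with probability 28%.

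**Simulation.** One fund, one wave, 40,000 runs. From the documents: 300 surveys, 8% women, 10% non-Caucasian. The following are assumptions, because the plan gives no rule:

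- A match means that both shares are non-significant at two-sided 5% by z-test.
- Up to six extra batches of 50 are added, stopping at the first match.
- Gender and race are independent, and age is not modelled.
- A targeted batch yields 16% women or 20% non-Caucasian for whichever group is short.

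| Share reached by the method (women / non-Caucasian) | Match at first 300 | Match after extension, same method | Match after extension, targeted |
|---|---|---|---|
| 8% / 10% (representative) | 0.92 | 0.98 | 0.99 |
| 6% / 7.5% | 0.59 | 0.68 | 1.00 |
| 5% / 7% | 0.33 | 0.38 | 1.00 |
| 4% / 5% (half the true share) | 0.03 | 0.03 | 1.00 |

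With only two targeted batches the last row reaches 0.80.

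Other match rules give the same pattern. With a match defined as within 3 percentage points, the 6% / 7.5% method goes from 0.53 to 0.76 by the same method and to 1.00 if targeted. With a 2-point rule, a truly representative method goes from 0.57 to 0.91 by the same method. The conclusion in that case is correct, but repeated looks still raise the match rate.

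**Response rate.** The only membership figure per fund is 10,200 (Section 9.2), which gives 300/10,200 = 2.9%. That figure is the estimate for the administrative data, which include retired members (Section 9.3), whereas surveys go to active members (Section 5). It is therefore not a reliable denominator. The documents give no better one.

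**The case against.** A reader might infer that collection continues until the sample matches, so that the check passes by construction. The documents do not support that reading.

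- Section 8.1 speaks of encouraging further collection. It sets no quota, no matching target and no rule to continue until one is met. Participation is voluntary and anonymous, so individual non-responders cannot be pursued.
- There is no pass mark. Section 9.1 says there is no formal hypothesis testing, Section 9.3 says only that the comparison helps the assessment, and the success criterion in Section 3 does not name representativeness.
- Continuing with the same biased method leaves the bias visible, as the table shows. Only a targeted extension brings the match close to certainty, and the protocol does not describe one.

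It can also be argued that monitoring with reminders is part of the procedure under test, and that the final sample is the right one for exploring respondent bias.

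All of this stands, and it limits the point. It does not remove it. If the monitored procedure is what is being tested, the extensions are part of that procedure and need to be reported. Targeting remains open to the funds, and a push prompted by under-representation could plausibly lead to it.

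On timing, the follow-up wave has its window, and the baseline wave must end before the intervention starts (Section 6.1.2) within the May 2022 to May 2023 period. What is missing is only a stated closing date for baseline. On the invited group, most of the text says all members; one phrase disagrees.

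**Conclusion.** The point holds in a limited form. Respondent demographics can prompt more collection and are then used to judge the recruitment methods, with no separate view of the earlier surveys and no report of the pushes. The comparison is therefore biased toward a favourable reading.

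Under the stated assumptions the bias is small when a clearly biased method simply continues (0.03 to 0.03; 0.33 to 0.38), moderate when the method is mildly biased (0.59 to 0.68), and large when extension targets missing groups (up to about 1.00). Which case applies cannot be known from the documents. The match rules, batch sizes and response shares are illustrations, not features of the plan.

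No endpoint definition and no stated success criterion is affected. What is affected is what the trial can say about survey feasibility. The inconsistent invited group and the absence of a response rate weaken the same conclusion.

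**What to change.** - **Section 9.3.** For each fund and wave, show the age, gender and race comparison side by side for (a) surveys received before the first extension prompted by count or demographics and (b) the final sample, with the number of surveys in each. Assign surveys by submission date, or by collection date for paper forms. Base the conclusion about the recruitment methods on both.
- **Section 8.1, extensions.** Log the date, channel and any targeting of each extra invitation round, and report the number of rounds.
- **Section 8.1, invited group.** Bring the sentence about inviting a representative sample into line with the invitation to all members used elsewhere.
- **Response rate.** Have each fund record the approximate number of members invited, and report completed/invited by fund and wave, labelled as approximate.
- **Timing.** State a closing date for the baseline wave. The follow-up wave already has its Day 180±30 window.

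Monitoring can continue and no survey is discarded. The cost is some protocol and SAP wording, a short log and one extra table. The denominator will be rough, because newsletters, verbal invitations and shared links do not give an exact count. Set (a) may be small if an extension comes early, and the feasibility result may look less favourable.
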